For the first secondary efficacy objective: With group vaccine efficacy of 65% but expecting conservatively reduced ERs of RT-PCR confirmed influenza cases due to matched strains of 2.5% among subjects in the non-influenza comparator group and 0.9% among the aQIV group then 144 events are estimated with power approximately 88.5% to show the absolute efficacy of aQIV versus non-influenza comparator, using a margin of 40% for lower bound of the 95% CI.		
Assuming a drop-out rate of 10%, approximately 10,692 subjects \geq 65 years, 5,346 per vaccine group will be randomized to receive either aQIV or non-influenza comparator (Boostrix®) in a 1:1 allocation ratio, stratifying by age groups: \geq 65 to 74 and \geq 75 years of age and by the presence or absence of medical co-morbidity (see Section 5.1.2, Screening for assessment of comorbidity and risk of complications)		

² The attack rate of 3.5% is estimated based on the attack rate published in placebo controlled studies (DeVilliers, 2009; Treanor, 2011; Frey, 2009)

Name of Sponsor: Seqirus UK Ltd.	Protocol number: V118_18	Generic name of study vaccine(s): MF59-adjuvanted Quadrivalent Subunit Inactivated Egg-derived Influenza Vaccine Tetanus Toxoid, Reduced Diphtheria Toxoid and Acellular Pertussis Vaccine, Adsorbed
--	------------------------------------	---

from influenza).

Sample Size for Secondary Immunogenicity Objective (Immunogenicity Subset):

The immunogenicity objective is considered as secondary and so no alpha adjustment for multiplicity will be done for the analysis therefore a significance level of 5% (2-sided) or 2.5% (1-sided) was used for sample size calculation.

Using the following assumptions from the V70_27 study in elderly adult subjects: specifically after aTIV vaccination, seroconversion rates, H1N1: 77%, H3N2: 74% and B: 47%, and percentages of subjects with a HI titer ≥ 40 , H1N1: 91%, H3N2: 99%, B: 64% (Table 1).

With samples analyzed from 1,362 subjects (1,226 evaluable subjects assuming a rate of 10% for missing data) in the aQIV group there will be at least 80% power to evaluate CBER criteria with all four strains contained in aQIV.

Table 1: CBER criteria for subjects ≥ 65 years of age

Strain	π_i (proportion in aQIV, based on data of V70_27)	π_0 (CBER threshold)	Sample size for aQIV	Marginal Power
Proportion of subjects with Seroconversion				
H1N1	77%	30%	1226	99%
H3N2	74%	30%	1226	99%
B strains	47%	30%	1226	99%
Proportion of subjects with HI titer ≥ 40				

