8.4.3.2.3 Statistical Methods

Similarly to the primary efficacy objectives, the PH model will be used to estimate absolute vaccine efficacy for secondary objectives 1-4. Evaluation of the key secondary objective will be done according to the conditional testing procedure. Absolute efficacy of aQIV with respect to the culture confirmed matched influenza will be demonstrated only providing successful demonstration of the primary objective (absolute efficacy with respect to RT-PCR-confirmed influenza regardless of antigenic match). This conditioning allows testing of both primary and key secondary efficacy objectives on the same significance level alpha.

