8.5 Sample Size and Power Considerations of Primary and Secondary Objectives

Efficacy objectives:

Sample size and power consideration for the aQIV efficacy objective is based on criteria for demonstrating efficacy in placebo controlled studies provided in CBER guidance, specifically that the study should be powered to assess the lower bound of the two-sided 95% CI of vaccine effectiveness, anticipated to be substantially above zero. This study is planned using a group sequential design. The power of Cox Regression which is planned to be used for analysis is dependent on the overall number of influenza cases, so the sample sizes on number of subjects described in this section is provided more for operational reasons. Additional information on the planning of number of subjects that may need to be enroled if it is decided to continue enrolment after interim analyses is described in [Section 8.6](#).

For the primary efficacy objective: with 1-sided alpha of 2.5% and assuming an attack rate of influenza of 3.5% among subjects enroled in the non-influenza comparator group and 1.4% among the aQIV group, i.e. 60% assumed vaccine efficacy for aQIV, 238 events (i.e. 4,860 subjects per group under the assumed ERs) are needed with 86.5% power to show the absolute efficacy of aQIV versus non-influenza comparator, in preventing first occurrence RT-PCR-confirmed influenza A and/or B, due to any strain of influenza regardless of antigenic match to the strains in aQIV, in subjects ≥ 65 years of age, using a margin of 40% for lower bound of the CI for absolute vaccine efficacy.

For the first secondary efficacy objective: with a group vaccine efficacy of 65% but expecting conservatively reduced event rates of influenza cases due to matched strains of 2.5% among subjects in the non-influenza comparator group and 0.9% among the aQIV group then 144 events has estimated power approximately 88.5% to show the absolute efficacy of aQIV versus non-influenza comparator, using a margin of 40% for lower bound of the CI.

Assuming a drop-out rate of 10%, approximately 10,692 subjects \geq 65 years, 5,346 per vaccine group will be randomized to receive either aQIV or non-influenza comparator (Boostrix®) in a 1:1 allocation ratio, stratifying by age (\geq 65 to 74 and \geq 75 years of age), study site and by low vs high risk of influenza complications (score <50 vs \geq 50).

Immunogenicity objective:

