Table 8.6-1 shows the needed total number of cases at each stage of the two-stage design together with boundaries for early stopping for futility or efficacy, calculated on p-value scale using the cumulative error spending function. With 1/2 information collected at the stage of interim analysis (that is, with exactly 119 confirmed ILIs) the trial would stop early for futility at this stage in case a p-value higher than 0.35022 is observed, or it would stop early for efficacy if the p-value is lower than 0.00625. Otherwise the trial will be continued and more subjects will be enrolled. The actual boundaries used for decision making would depend on number of confirmed ILIs occurring and reported for Interim Analysis.

Table 8.6-1: Example of a Two Stages Group-Sequential Design

	Stage 1 First Interim	Stage 2 Final
Number of Events	119	238
Alpha Boundary on p-value scale (equivalent to Type 1 error, 1-sided), early stopping for efficacy	0.00625	0.02275
Beta Boundary on p-value scale (equivalent to Type 2 error, 1-sided), early stopping for futility	0.35022	0.02275

The stopping rules given above are statistical and should be completed with clinical and strategic stopping rules that allow the DMC to make a decision on a broader picture of the data which includes safety endpoints and the other endpoints of the study. Another interim look at the data with appropriate adjustment of type 1 error might be recommended before reaching the targeted 238 cases.

Further details of the statistical methods are provided in the SAP and more information regarding clinical or strategic stopping rules will be provided in the DMC charter.

For the interim analyses, if needed a restricted unblinding will be done, i.e. only independent DMC members and unblinded individuals responsible for the analyses will receive access to the randomization codes and unblinded data for the purpose of preparing the interim analyses (further information on handling of the blinding for the interim analyses can be found in [Section 3.3](#)). The results of the interim analyses will be used only for DMC purposes and will not be reported in a Clinical Study Report (CSR).

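### The 88.5% power quoted for the key secondary is a stand-alone figure; behind a primary with 86.5% power, the written procedure gives at most 86.5% and about 74–83% on the plan's inputs

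*Protocol*

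**What the plan says.** Protocol 8.5 gives two power figures for efficacy. For the primary, 238 events "are needed with 86.5% power to show the absolute efficacy of aQIV" at 60% efficacy against a 40% margin. For the key secondary, at 65% efficacy against the same margin, "then 144 events has estimated power approximately 88.5% to show the absolute efficacy of aQIV". SAP 5 carries the same two figures, and the synopsis has "then 144 events are estimated with power approximately 88.5"%. In none of the three places is 88.5% called marginal, and none mentions the primary's role in the key secondary.

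Protocol 8.4.3.2.3 sets the testing order: efficacy against matched strains "will be demonstrated only providing successful demonstration of the primary objective". On that basis both are tested at the same alpha.

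Protocol 8.6 and SAP 14.1 allow an efficacy stop before 238 cases. In the worked example with 119 cases, "it would stop early for efficacy if the p-value is lower than 0.00625". SAP 12.2 reduces the level for secondary analyses if the trial continues past an interim. Neither document gives the key secondary's level, or the data it would use, if the trial stops for efficacy.

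**The concern.** A claim that needs the primary to succeed cannot succeed more often than the primary, yet the plan prints 88.5% behind 86.5%. A reader of Protocol 8.5 would take 88.5% as the planned chance of demonstrating the key secondary. An early stop can lower that chance further, because fewer matched cases may then be available. Protocol 8.2.2.2 makes this the only secondary efficacy objective tested for success, so its planning probability should describe the procedure that will be run. Type I error and the primary claim are not at stake.

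**Working it through.** **Inputs.** From Protocol 8.5: one-sided alpha 0.025; primary HR 0.40 with 238 events; key secondary HR 0.35 with 144 events; null HR 0.60; 1:1 allocation. From Table 8.6-1: efficacy p < 0.00625 (z = 2.498) and futility p > 0.35022 (z = 0.385) at 119 cases; final p < 0.02275 (z = 2.000). Assumed here: information = events/4, and correlation √(144/238) = 0.778 between the two statistics, because matched cases are treated as a subset of primary cases.

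**1. Reproduce the plan's figures.** Drift = ln(0.60/HR) × √(events/4).

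- Primary: ln(0.60/0.40) × √(238/4) = 0.4055 × 7.714 = 3.128.
- Key secondary: ln(0.60/0.35) × √(144/4) = 0.5390 × 6 = 3.234.
- Fixed test at 0.025: Φ(3.128 − 1.960) = 87.9% and Φ(3.234 − 1.960) = 89.9%.
- Fixed test at 0.02275: 87.0% and 89.1%.
- Each objective given its own Table 8.6-1 two-stage design (119/238 and 72/144): **86.5%** and **88.6%**.

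The last line matches both printed figures, so 88.5% is a stand-alone power.

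**2. Ceiling.** P(primary and key secondary) ≤ P(primary) = 86.5%. The printed figure exceeds this by 88.5 − 86.5 = 2.0 points, and no assumption about correlation is needed.

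**3. Which interim boundary.** The spending function in Protocol 8.6 gives, at half information, 2[1 − Φ(2.2414/√0.5)] = 0.0015 (z = 2.963), not the table's 0.00625. The matching final z is 1.969 and the futility z is 0.291. Both sets are carried below.

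**4. Size of the early stop.** Primary drift at 119 cases is 0.4055 × √(119/4) = 2.212. The probability of stopping for efficacy is Φ(2.212 − 2.498) = 39% under the table, or Φ(2.212 − 2.963) = 23% under the spending function. Matched cases pro rata: 144 × 119/238 = 72. Key secondary drift at 72 cases is 0.5390 × √(72/4) = 2.287, so its stand-alone power there is 63% at 0.025, 42% at 0.00625 and 25% at 0.0015.

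**5. Joint power.** Normal simulation, 4 million draws, both statistics at half and full information, futility rule applied:

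| Quantity | Table 8.6-1 | Spending function |
|---|---|---|
| Primary succeeds | 86.5% | 87.0% |
| Both succeed, key secondary always on 144 cases | 82.2% | 83.0% |
| Both succeed, stop at 119 cases, key secondary at 0.025 on 72 | 80.4% | 82.6% |
| Both succeed, stop at 119 cases, key secondary at stage boundary on 72 | 74.0% | 76.1% |

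**6. Sensitivity.** The stated rates imply 4,860 × (2.5% + 0.9%) = 165 matched cases rather than 144. With 165 cases and HR 0.36, the last two rows become about 82–84% and 77–79%. With correlation 0.6, the 0.025 row falls to about 76–81%. With the interim at 60–75% information, it is about 79–82%.

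**The case against.** Quoting power objective by objective is ordinary practice. The 88.5% reproduces, and its sentence already ties it to 144 events. A reader might infer an arithmetic error; there is none. The same section even heads its immunogenicity column as marginal power. That shows the label was at hand, but it was not applied to the efficacy figure.

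A reader might also infer that 88.5% belongs to a single look with every event in hand and so ignores the interim. The documents do not support this. A fixed 144-event test gives 89–90%, and the closest match (88.6%) allows the key secondary its own look at 72 of 144 cases. What the figure leaves out is the dependence on the primary.

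Nor can 80–83% be put forward as the plan's own corrected value. It needs the key secondary to be tested at the full 0.025 at an efficacy stop, which no section says. The same-alpha wording in Protocol 8.4.3.2.3, read as the stage boundary, gives 74–76%. The 72 matched cases are also an assumption. Swabs may be collected to Day 366 (Protocol 3.9), and the interim inputs listed in SAP 14.1 do not name culture or antigenic-match results. If matched cases continued to accrue after a stop, the result would move towards the 82–83% row.

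Finally, study success rests on the primary, and SAP 12.2 states its success criterion for the secondary efficacy objectives generally. This limits the weight of the point. None of these arguments lifts the ceiling: with the stated primary power, success on both cannot reach 88.5%.

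**Conclusion.** The point holds as a mislabelled planning figure. The 88.5% is a correct marginal power shown without qualification for an objective that can succeed only after the primary. The firm statement is the ceiling of 86.5%, which follows from the testing order and the plan's own primary power.

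Below that ceiling the value depends on rules the documents leave open. It is about 82–83% from the testing order alone; 80–83% with an early stop and a 0.025 test (about 6–8 points under the printed figure); and 74–76% with the stage boundary (about 12–15 points under). These rest on information = events/4, the assumed correlation, an interim at 119 cases and, for the last two, about 72 matched cases analysed. No single replacement figure is justified until the interim boundary and the key secondary's rule at a stop are fixed. The point is worth correcting, but the design's validity does not depend on it.

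**What to change.** 1. In Protocol 8.5, the synopsis and SAP 5, label 88.5% as marginal, that is, not conditional on the primary.
2. State in the protocol and SAP 12.2 the key secondary's significance level and data cut if the trial stops for efficacy.
3. Reconcile the interim boundary: 0.00625 in Table 8.6-1 and SAP Table 1, against about 0.0015 from the written spending function.
4. Then compute one joint power, the probability that the primary succeeds and the key secondary succeeds under the stated rule, and report it beside the marginal figure with its correlation assumption. Until then, say that it is at most 86.5%, and about 74–83% depending on the rule.

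The cost is a short simulation, a sentence on the rule and revised wording in three places. Enrolment and conduct do not change. The only downside is a less favourable stated figure.

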Name of Sponsor: Seqirus UK Ltd.	Protocol number: V118_18	Generic name of study vaccine(s): MF59-adjuvanted Quadrivalent Subunit Inactivated Egg-derived Influenza Vaccine Tetanus Toxoid, Reduced Diphtheria Toxoid and Acellular Pertussis Vaccine, Adsorbed
microneutralization).		

Name of Sponsor: Seqirus UK Ltd.	Protocol number: V118_18	Generic name of study vaccine(s): MF59-adjuvanted Quadrivalent Subunit Inactivated Egg-derived Influenza Vaccine Tetanus Toxoid, Reduced Diphtheria Toxoid and Acellular Pertussis Vaccine, Adsorbed
Number of Subjects Planned:		
As described in the study design section this study will employ group sequential design and therefore the total study size (and study duration) will depend on the number of RT-PCR confirmed influenza cases observed during the influenza seasons (see Section 3.7, DMC and Section 8.6, Interim Analysis).		
The sample size, among other factors, depends mainly on the number of PCR-confirmed influenza cases observed during the influenza seasons so the overall number of subjects to be recruited may change and enrolment over multiple seasons may be required to ensure 238 PCR-confirmed influenza cases have occurred and/or based on the results of the interim analysis for efficacy and futility. It is anticipated that in order to obtain 238 cases, including a drop-out rate of 10%, approximately 10,692 subjects \geq 65 years, will need to be enrolled into the trial. Approximately 5,346 subjects will be enrolled per vaccine group will be randomized to receive either aQIV or non-influenza comparator (Boostrix [®]) in a 1:1 allocation ratio, stratifying by age (\geq 65 to 74 and \geq 75) and by comorbidity status (at risk/not at risk, see Section 5.1.2, Screening).		
Specimens from those collected during the immunogenicity season will be randomly selected in a 4:1 ratio for analysis. In total approximately 1,702 of the up to 2800 samples collected are planned to be included the analysis (1,362 aQIV; 340 Boostrix). The serum samples may also be analyzed to facilitate the estimation of immune correlate of protection.		

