where HR is defined as hazard ratio of the incidence of protocol defined ILI in aQIV versus a non-influenza comparator that will be estimated by the proportional hazards model. More details on the analysis methods will be described in the Statistical Analysis Plan (SAP).		
The study is successful if the lower-limit (LL) of the two-sided 95% confidence interval (CI) (to be adjusted for one interim analysis) of absolute vaccine efficacy endpoint > 0.4 . In case another interim analysis is necessary the type 1 error alpha and hence the CI will be adjusted.		
Overall Study Success Criteria:		
The study is successful if the primary efficacy objective is achieved.		
Sample Size and Power Calculation for Primary Objective:		
Sample size and power consideration for the aQIV efficacy objective is based on criteria for demonstrating efficacy in placebo controlled studies provided in CBER guidance, specifically that the study should be powered to assess the lower bound of the two-sided 95% CI of vaccine effectiveness, anticipated to be substantially above zero.		
This study is planned using a group sequential design. The power of Cox Regression which is planned to be used for analysis is dependent on the overall number of RT-PCR		

Name of Sponsor: Seqirus UK Ltd.	Protocol number: V118_18	Generic name of study vaccine(s): MF59-adjuvanted Quadrivalent Subunit Inactivated Egg-derived Influenza Vaccine Tetanus Toxoid, Reduced Diphtheria Toxoid and Acellular Pertussis Vaccine, Adsorbed
confirmed influenza cases, so the sample sizes on number of subjects described in the sections above is provided more for operational reasons. Additional information is described in Section 8.6, Interim Analysis .		
For the primary efficacy objective: with 1-sided alpha of 2.5% (adjusted for possible interim analysis) and assuming an attack rate of influenza of 3.5% among subjects enroled in the non-influenza comparator group and 1.4% among the aQIV group, i.e. 60% assumed vaccine efficacy for aQIV, 238 events (i.e. 5,346 subjects per group under the assumed event rates (ER)) are needed with 86.5% power to show the absolute efficacy of aQIV versus non-influenza comparator, in preventing first occurrence RT-PCR confirmed influenza A and/or B, due to any strain of influenza regardless of antigenic match to the strains in aQIV, in subjects \geq 65 years of age, using a margin of 40% for lower bound of the CI for absolute vaccine efficacy ² .		

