Anti-HA antibody will be measured using a validated haemagglutination inhibition (HI) assay with egg-derived HA antigens from homologous strains of the virus.

The immunogenicity objective is considered as secondary and so no alpha adjustment for multiplicity will be done for the analysis therefore a significance level of 5% (2-sided) or 2.5% (1-sided) was used for sample size calculation. One season in which at least 2800 subjects are anticipated to be enrolled will be selected for the collection of immunogenicity samples. Samples from approximately 2800 subjects participating in the immunogenicity season will be obtained. In order to maintain the study blind blood samples from an equal number of subjects participating in both treatment groups will be collected at Day 1 (baseline) and Day 22 (visit 3).

After all of the specimens have been obtained a subset of samples from those collected will be randomly selected on a 4:1 ratio for analysis. In total approximately 1,702 samples are planned to be included the analysis (1,362 aQIV; 340 Boostrix). The details and the guidelines regarding the selection process of these samples can be found in the SAP.

Following assumptions from the V70_27 study in elderly adult subjects were used: specifically after aTIV vaccination, seroconversion rates, H1N1: 77%, H3N2: 74% and B: 47%, and percentages of subjects with a HI titer \geq 40, H1N1: 91%, H3N2: 99%, B: 64%.

With samples from at least 1,362 enroled subjects (1,226 evaluable subjects assuming a rate of 10% for missing data in the aQIV group) there will be enough power to evaluate achievement of CBER criteria with all four strains contained in the vaccine (see [Table 8.5-1](#)).

Table 8.5-1: Power to assess CBER criteria for subjects ≥ 65 years of age

Strain	π_i (proportion in aQIV, based on data of V70_27)	π_0 (CBER threshold)	Sample size for aQIV	Marginal Power
Proportion of subjects with Seroconversion				
H1N1	77%	30%	1226	99%
H3N2	74%	30%	1226	99%
B strains	47%	30%	1226	99%
Proportion of subjects with HI titer $\geq 1:40$				
H1N1	91%	60%	1226	99%
H3N2	99%	60%	1226	99%
B strains	64%	60%	1226	82%

Safety objectives:

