4. RANDOMIZATION AND BLINDING

4.1 Method of Group Assignment and Randomization

Approximately 10,620 subjects ≥ 65 years will be randomized to receive either aQIV or non-influenza comparator in a 1:1 allocation ratio, stratifying according to age (≥ 65 to 74 and ≥ 75 years), study site and comorbidity status (at risk/not at risk). Each randomized subject will be automatically assigned a unique Subject identification (ID) and Pack ID indicating the assigned treatment. The Subject ID will be the subject's unique identification number for all CRFs and associated study documentation that will be used for duration of the study.

The Subject ID consists of a 7-digit number resulting from the combination of the site number, and the subject's order of randomization at the site. After randomization, the Screening Number ceases to be used and remains in the Screening and Enrolment Log only. The list of randomization assignments is produced by the Interactive Response Technology (IRT) service provider and approved by Seqirus or delegate.

One season in which at least 2800 subjects are anticipated to be enrolled will be selected for the collection of immunogenicity samples. Samples from first 2800 subjects participating in the selected season (1,400 from each treatment arm) will be collected at Day 1 (baseline) and Day 22 (Visit 3). In order to maintain the study blind equal numbers of subjects from both treatment groups will be asked to provide blood specimens. After all of the specimens have been obtained, a subset of subjects with both samples collected will be randomly selected on a 4:1 ratio (1,362 aQIV; 340 Boostrix) for the purpose of completing the analysis of the immunogenicity objectives. The selected subjects will constitute the Immunogenicity Set. The samples from the selected subjects will be randomized into batches for HI testing in such a way that both samples from one subject are contained within one batch, but the sequence of samples is random. See [section 4.2](#) for discussion of maintaining the study blind with respect to the selected Immunogenicity Set subjects. Serum samples from subjects with RT-PCR confirmed influenza, along with a subset of subjects who did not have RT-PCR confirmed influenza, may be tested to estimate the correlate of protection. The serologic component of the correlate of protection will be measured using either a validated haemagglutination inhibition (HI) and/or other immunological assays (such as microneutralization).

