5. SAMPLE SIZE AND POWER CONSIDERATIONS

Efficacy objectives:

Sample size and power consideration for the aQIV efficacy objective is based on criteria for demonstrating efficacy in placebo controlled studies provided in CBER guidance, specifically that the study should be powered to assess the lower bound of the two-sided 95% CI of vaccine effectiveness, anticipated to be substantially above zero. This study is planned using a group sequential design. The power of Cox Regression which is planned to be used for analysis is dependent on the overall number of influenza cases, so the sample sizes on number of subjects described in this section is provided more for operational reasons. Additional information on the planning of number of subjects that may need to be enrolled if it is decided to continue enrolment after interim analyses is described in [Section 8.6](#).

For the primary efficacy objective: with 1-sided alpha of 2.5% and assuming an attack rate of influenza of 3.5% among subjects enrolled in the non-influenza comparator group and 1.4% among the aQIV group, i.e. 60% assumed vaccine efficacy for aQIV, 238 events (i.e. 4,860 subjects per group under the assumed ERs) are needed with 86.5% power to show the absolute efficacy of aQIV versus non-influenza comparator, in preventing first occurrence RT-PCR-confirmed influenza A and/or B, due to any strain of influenza regardless of antigenic match to the strains in aQIV, in subjects ≥ 65 years of age, using a margin of 40% for lower bound of the CI for absolute vaccine efficacy.

For the first secondary efficacy objective: with a group vaccine efficacy of 65% but expecting conservatively reduced event rates of influenza cases due to matched strains of 2.5% among subjects in the non-influenza comparator group and 0.9% among the aQIV group then 144 events has estimated power approximately 88.5% to show the absolute efficacy of aQIV versus non-influenza comparator, using a margin of 40% for lower bound of the CI.

Assuming a drop-out rate of 10%, approximately 10,692 subjects ≥ 65 years, 5,346 per vaccine group will be randomized to receive either aQIV or non-influenza comparator (Boostrix®) in a 1:1 allocation ratio, stratifying by age (≥ 65 to 74 and ≥ 75 years of age), study site and by low vs high risk of influenza complications (score < 50 vs ≥ 50).

Immunogenicity objective:

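### The stated sample-size figures do not reconcile: 238 events are tied to both 5,346 and 4,860 subjects per group, the SAP gives two randomisation totals, and the 10% drop-out allowance covers 9.1% full loss

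*Protocol*

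**What the plan says.** **Events and subjects per group.** SAP section 5, like Protocol section 8.5, has "238 events (i.e. 4,860 subjects per group under the assumed ERs) are needed with 86.5% power". The synopsis, under the sample size and power calculation for the primary objective, has "238 events (i.e. 5,346 subjects per group under the assumed event rates (ER)) are needed with 86.5% power". The inputs are the same in each place: "assuming an attack rate of influenza of 3.5% among subjects enroled in the non-influenza comparator group", with a rate of 1.4% under aQIV, which is a vaccine efficacy of 60%.

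**Total enrolment.** Protocol section 8.5 and SAP section 5 both state "Assuming a drop-out rate of 10%, approximately 10,692 subjects", 5,346 per group. The synopsis, under the number of subjects planned, says that obtaining 238 cases, "including a drop-out rate of 10%, approximately 10,692 subjects", needs this enrolment. SAP section 3 also gives 10,692. SAP section 4.1 instead has "Approximately 10,620 subjects" to be randomised, and SAP section 8.5 repeats that total.

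**Evaluable subjects.** The safety sample-size statements in the synopsis, Protocol section 8.5 and SAP section 5 all use 4,860 evaluable subjects per group.

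**Other allowances for missing data.** For immunogenicity, Protocol section 8.5 has 1,362 subjects giving "1,226 evaluable subjects assuming a rate of 10% for missing data in the aQIV group". For solicited safety, the synopsis has 1,053 per group giving at least 1,000 evaluable with up to 5% missing.

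**The concern.** One number, 5,346, stands in the synopsis both as the size that produces 238 events and, in a following paragraph, as the size after the drop-out allowance. It cannot be both at the same attack rates. The SAP carries two randomisation totals, and only one agrees with the protocol. The step from 4,860 to 5,346 also looks like adding 10% to the evaluable number, which does not leave 4,860 after a 10% loss.

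At stake is the accuracy of the enrolment target, the evaluable number and the expected case count, which an assessor would try to reproduce early. The primary test is not at stake, because analysis is triggered by cases and not by enrolment.

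**Working it through.** **Inputs.** Attack rates 3.5% and 1.4%, 238 events, 4,860 per group, 10% drop-out and 10,692 in total are from Protocol section 8.5. The 5,346 tied to 238 events is from the synopsis. The 10,620 is from SAP sections 4.1 and 8.5.

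**1. Reproduce the plan's figures.**
- One subject per group gives 0.035 + 0.014 = 0.049 expected cases.
- Subjects per group for 238 cases: 238 / 0.049 = 4,857, against 4,860 stated.
- Cases from 4,860 per group: 4,860 × 0.049 = 238.1.
- Drop-out: 4,860 × 1.1 = 5,346 exactly, and 2 × 5,346 = 10,692. The plan's total is reproduced by multiplying by 1.1.

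**2. The synopsis figure.** Taken as the evaluable number behind the events, 5,346 × 0.049 = 262.0 cases. That is 24 more than 238.

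**3. The SAP's second total.** 10,620 / 2 = 5,310 per group. This is neither 4,860 × 1.1 = 5,346 nor 4,860 / 0.9 = 5,400. The difference from 10,692 is 72 subjects, or 0.7%.

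**4. What each total delivers if 10% are lost and contribute no cases.**

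| Total | Evaluable per group | Expected cases |
|---|---|---|
| 10,620 | 5,310 × 0.9 = 4,779 | 4,779 × 0.049 = 234.2 |
| 10,692 | 5,346 × 0.9 = 4,811 | 4,811.4 × 0.049 = 235.8 |
| 10,800 | 5,400 × 0.9 = 4,860 | 4,860 × 0.049 = 238.1 |

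So 10,692 leaves 4,860 − 4,811 = 49 fewer evaluable per group than stated. The loss that it does cover is 1 − 4,860 / 5,346 = 9.1%. The gap to 10,800 is 108 subjects, or 1.0%.

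**5. How firm the case shortfall is.**
- With no loss, 10,692 gives 10,692 × 0.0245 = 262.0 cases.
- With 10% full loss it gives 235.8, so the 10% who drop out account for 262.0 − 235.8 = 26.2 expected cases.
- Reaching 238 needs (238 − 235.8) / 26.2, about 9%, of those cases to be observed.
- If drop-outs contributed half of theirs (an assumption, not in the documents), the total would be 235.8 + 13.1 = 248.9.

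**6. Effect on power if the analysis were run at 236 events.** The Schoenfeld approximation with hazard ratio 0.4 / 0.6 and one-sided alpha 0.025 gives 87.9% at 238 events and 87.6% at 236, a difference of about 0.3 points. It is used here only for that difference. The absolute level depends on the variance formula and is not part of this point.

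**7. The other allowances.** 1,226 / 0.9 = 1,362, where × 1.1 would give 1,349. 1,000 / 0.95 = 1,053, where × 1.05 would give 1,050. Both are divisions, so the documents use two rules.

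**The case against.** **The trial is event-driven.** The documents call the subject numbers approximate and operational, say that they may change, and run the trial to 238 cases subject to interim stopping. This stands, and it settles the severity. It does not explain why two figures are attached to one event count, or why the SAP has two totals.

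**Drop-outs are not lost to the analysis.** A reader might infer that 10,692 fails to deliver 238 cases under the plan's own assumptions. The documents do not support that. Subjects who drop out are right-censored (Protocol section 8.4.2.2.3, SAP section 12.1). The efficacy FAS takes anyone randomised and vaccinated who is observed for at least 21 days and provides efficacy data (Protocol section 8.3.4, SAP section 7.3). Someone leaving later can contribute a case, and about 9% of the drop-outs' expected cases would restore 238. The attack rates are also worded as rates among enrolled subjects. The figure of 236 is therefore conditional on full loss.

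**The divisions elsewhere are not like for like.** They concern missing serology and missing diary data, where a subject without data contributes nothing. This stands in part. It weakens the charge of inconsistency for case counts, but not for the 4,860 evaluable per group that the safety statements use.

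**The synopsis can be untangled.** It never calls 5,346 evaluable, and it says elsewhere that 5,346 includes drop-out. A careful reader can resolve it, but the parenthesis still differs from Protocol section 8.5 and SAP section 5.

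**Re-enrolment.** A reader might also infer that the re-enrolment formula should be divided by 0.9. That is not established. Protocol section 8.6 uses the assumed rates, but SAP section 14.1 uses the observed combined attack rate and does not state its denominator. If that rate is taken over enrolled subjects it already reflects drop-out, and a further division would over-inflate.

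**Conclusion.** The point holds as three mismatches among stated figures.

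1. The synopsis ties 238 events to 5,346 per group, while Protocol section 8.5 and SAP section 5 tie them to 4,860. The difference is 262 against 238 cases at the same rates. This rests only on the printed figures.
2. The SAP contradicts itself and the protocol: 10,692 in sections 3 and 5, 10,620 in sections 4.1 and 8.5. The gap is 0.7%, and 10,620 is not derived anywhere. This too needs no assumption.
3. The drop-out allowance covers 9.1% full loss, not 10%. At 10% full loss, 49 evaluable subjects per group are missing. The accompanying shortfall of about 2 cases is an upper bound, because it assumes that drop-outs contribute none.

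It would be wrong to read this as a loss of power or validity. The decision depends on reaching 238 cases, the enrolment gap is about 1%, and even analysing at 236 events would cost about 0.3 points of power. It is a minor correction of stated numbers.

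**What to change.** Text changes only, with no added enrolment:

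- **Synopsis, sample size and power for the primary objective:** attach 238 events to 4,860 evaluable subjects per group, and keep 5,346 for the number after the drop-out allowance.
- **SAP sections 4.1 and 8.5:** replace 10,620 with the single total used elsewhere, 10,692.
- **Synopsis, Protocol section 8.5 and SAP section 5:** keep 10,692 but state that it covers 9.1% of subjects being fully lost. If the sponsor prefers to state cover for 10% full loss, the figure is 5,400 per group, 10,800 in total.

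The cost is a few sentences in each document. No change to the re-enrolment formula is proposed on this ground.
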